### 9.4.4.2 Safety

#### **Safety Population:**

The safety population will include all non-censored subjects who received the Tritanium® Acetabular Shell.

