### 9.2 Safety Parameters

### 9.2.1 Safety Parameters

Safety parameters will include:

- All AEs reported
- Radiographic stability at each postoperative visit
- Revision or removal rates

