### 9.2.2 Safety Analysis

All AEs will be listed, tabulated and summarized by event, number and percent of cases/subjects. AE rates and 95% confidence intervals will be presented.

For categorical variables, such as radiographic stability, the number and percent in each category will be presented.

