### 9.4.4.3 Survival Analysis

#### **Modified intent to treat population:**

Subjects enrolled in the study who received the Tritanium® Acetabular Shell will be included in the survival analysis.

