#### 9.4.4.4 Censored Cases

In the event that a protocol deviation occurs which could affect patient outcome, the data for the affected patient will be censored from the Efficacy and Safety Patient Populations. All cases that fall into this category will be reported separately.

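### The safety population drops shell recipients who had an undefined type of protocol deviation, so the safety rates need not describe everyone exposed

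*Combined protocol and SAP*

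**What the plan says.** Section 9.4.4.2 reads "The safety population will include all non-censored subjects who received the" Tritanium shell. Section 9.4.4.4 explains the censoring: if "a protocol deviation occurs which could affect patient outcome", then "the data for the affected patient will be censored from the Efficacy and Safety Patient Populations". It adds: "All cases that fall into this category will be reported separately".

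Section 9.2.2 says "All AEs will be listed, tabulated and summarized by event, number and percent of cases/subjects" and "AE rates and 95% confidence intervals will be presented", without naming a population. The safety parameters in Section 9.2.1 also include radiographic stability and "Revision or removal rates".

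Section 9.4.4.3 applies no such filter to the survival analysis: enrolled subjects given the Tritanium "Acetabular Shell will be included in the survival analysis".

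**The concern.** A safety population should normally contain everyone exposed to the device. Here a subject who carries the implant can be taken out of both numerator and denominator. The rule removes the patient's data without limit of time, so events before the deviation would go too.

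The trigger is a property of the deviation, but it cannot be applied reproducibly. The deviation list in Section 11.6 is open-ended and marks no item as affecting outcome. The Notice of Protocol Deviation form in Appendix E records the type of deviation and the reason for it, and shows no item for effect on outcome. No section says who classifies, or when. In an open study of a single device, the judgement could be made after an event has been seen.

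The safety rates are to be set against the historical control and published rates (Sections 2.2 and 12.3). That comparison needs a denominator that two analysts would derive identically. The report could also show two revision figures, one from the safety section and one from the survival analysis, resting on different subjects.

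**Working it through.** **Reading the sections together**

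1. Sections 9.4.4.2 and 9.4.4.4 make the safety set the implanted subjects minus those censored for a deviation.
2. Sections 11.6 and 12.4 and the deviation form do not define the trigger. Section 12.4 foresees deviations made to protect a subject's health, and nothing exempts them from censoring.
3. Censored subjects need not be average. One listed deviation is enrolling a patient who fails eligibility. The exclusions in Section 4.2 include BMI of 40 or more and active or suspected latent infection. The product labeling (Appendix F) warns of fixation loss or device failure in obese patients and lists infection as a contraindication. Some censored cases could therefore carry higher risk. Other deviations could carry equal or lower risk.

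**Size**

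The plan gives no adverse event rate, no deviation rate and no figure of its own on this point. The only input from the documents is the 240 planned implanted cases (Section 9.4.2). Assumed inputs:

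- d, the share censored: 5% (12 of 240) or 10% (24 of 240)
- RR, the event risk in censored relative to retained cases: 0.5 to 5
- r, the rate in retained cases: 10% for illustration

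All-implanted rate = r × [(1 − d) + d × RR], so reported ÷ all-implanted = 1 ÷ [(1 − d) + d × RR]. For d = 5% and RR = 2 this is 1 ÷ (0.95 + 0.10) = 0.952.

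| RR | Ratio, d = 5% | Ratio, d = 10% | All-implanted rate at r = 10%, d = 5% | Same, d = 10% |
|---|---|---|---|---|
| 0.5 | 1.026 | 1.053 | 9.75% | 9.5% |
| 1 | 1.000 | 1.000 | 10.0% | 10.0% |
| 2 | 0.952 | 0.909 | 10.5% | 11.0% |
| 3 | 0.909 | 0.833 | 11.0% | 12.0% |
| 5 | 0.833 | 0.714 | 12.0% | 14.0% |

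Bounds that need no RR suppose that none, or all, of the censored cases have the event: r(1 − d) to r(1 − d) + d. At r = 10% they are 9.5% to 14.5% for d = 5%, and 9.0% to 19.0% for d = 10%.

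For scale, the 95% confidence interval half-width at 10% is 1.96 × √(0.1 × 0.9 ÷ n). This is 3.9 points at n = 228 and 4.0 points at n = 216. The shifts for RR 2 to 5 are 0.5 to 2.0 points (d = 5%) and 1.0 to 4.0 points (d = 10%), so they reach but do not exceed sampling error. The reported interval does not allow for them.

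An invented example in counts: 12 censored cases with 3 events and 228 retained cases with 5 events. The safety population gives 5/228 = 2.2% (exact 95% CI 0.7% to 5.0%). All implanted cases give 8/240 = 3.3% (1.4% to 6.5%).

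**The case against.** The strongest reply is that the plan already limits the damage. Censored cases must be reported separately, so their data are disclosed. The survival analysis keeps all implanted subjects, so shell revision is covered there and the gap falls mainly on adverse event rates and radiographic summaries. Collection and reporting of adverse events are unaffected. Many listed deviations, such as missed visits or a wrong consent version, would not naturally be read as affecting outcome, so a 10% censored share may be high. Sections 9.2.2 and 9.4.4.2 can also be read together without contradiction: one says what is tabulated, the other for whom. The rates are wrong only if at least one implanted subject is censored, and the magnitude is entirely assumed.

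Most of this is fair, and it limits the severity. It does not repair the definition. The content of the separate report is unspecified and no pooled all-exposed adverse event rate is planned. A narrow reading of the trigger is the reader's inference, since the plan does not state one. Section 9.2.2 promises all adverse events, and a reader could not tell that some subjects are absent from the rates.

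A practical objection also has weight. Section 8.3 sends device-related events and reoperations to the sponsor within 24 hours, so classifying deviations before events are known may be difficult. That affects only the optional sensitivity analysis, not the main correction.

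**Conclusion.** The concern holds and should be fixed. As written, the plan removes from the safety population any implanted subject whose deviation meets an undefined test, and the planned safety rates would then not describe all exposed subjects. This follows from the text and needs no numerical assumption.

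The size and direction of any bias cannot be found from the documents. Across the assumed range, the reported rate runs from 1.05 down to 0.71 times the all-implanted rate, with no bias at equal risk. The documents also do not give the control study's safety-population rule, so the effect on that comparison is unknown. The safety analysis is descriptive, and neither the primary non-inferiority decision nor the sample size figures (142, 177, 240) depend on the safety-population rule.

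**What to change.** - In Section 9.4.4.2, delete *non-censored*, so that the safety population is all subjects or cases that received the Tritanium shell.
- In Section 9.4.4.4, delete *and Safety*. Keep the separate listing of deviating cases and state that it includes their adverse events.
- In Section 9.2.2, name the safety population, so that the adverse event rates, radiographic summaries and revision or removal rate use the same implanted subjects as Section 9.4.4.3.
- If the historical control made a similar exclusion, add the deviation-excluded rates as a supplementary sensitivity analysis. List the qualifying deviations, name the role that classifies them, and require classification before that subject's events are reviewed. Given the 24-hour reporting, this could be done by someone working from the deviation record alone, without the adverse event data.

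The same undefined trigger feeds the efficacy population in Section 9.4.4.1, which is a separate point.

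The cost is a few wording changes, one optional table, and an amendment submitted to the ethics committees or IRBs (Section 14). The data are already collected. Reported rates may become less favourable. If the control study excluded similar cases, the all-implanted rate alone would be less comparable with it, which the sensitivity analysis addresses.

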### 9.4.4.3 Survival Analysis

#### **Modified intent to treat population:**

Subjects enrolled in the study who received the Tritanium® Acetabular Shell will be included in the survival analysis.

#### 9.4.4.4 Censored Cases

In the event that a protocol deviation occurs which could affect patient outcome, the data for the affected patient will be censored from the Efficacy and Safety Patient Populations. All cases that fall into this category will be reported separately.

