#### Adverse events that require time sensitive reporting:

An adverse event should be reported to the study sponsor (CSM or CSA) either by telephone/fax/email within 24 hours of the site's becoming aware of the event if any of the following apply:

- The AE is considered by the investigator to be device related or if the investigator is uncertain regarding the device related assessment;
- The AE required a reoperation of the study hip or a revision of any study hip components.

An AE eCRF must be completed by the investigator within 24 hours. If a SAE occurs, the de-identified source documentation must be uploaded to the Subject Binder of Stryker's Electronic Data Capture (EDC) system, within 24 hours of the investigative center's SAE awareness. See Section 11, Data Management, for additional details of Stryker's EDC system. These reports will be evaluated by Stryker to determine if a PER is required.

It is recommended that all other reportable adverse events are reported on eCRFs and submitted to Stryker within 2 weeks.

At the time of the initial report, the following information should be provided:

- Subject number
- A description of the event
- Date of onset
- Current status

- Whether study treatment was discontinued
- Investigator assessment of the association between the event and the study treatment

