### 9.1.4 Primary Efficacy Analysis

A case success is defined as no incidence of revision or removal of the acetabular component within 5 years. A 90% confidence interval of the success rate will be computed at 5 years postoperative. If the lower bound of this confidence interval is greater than 94%, the non-inferiority hypothesis will be supported. If the lower bound of this confidence interval is above 99%, the superiority hypothesis will be supported. The Kaplan-Meier survival curve of revision or removal of the acetabular component will also be displayed using SAS/PROC LIFETEST.

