# **9.4.3 Interim Analyses and early Stopping Considerations** No interim analysis is planned.

### 9.4.4 Efficacy Patient Populations

### 9.4.4.1 **Efficacy**

#### Per protocol population:

The study population for analysis will include all subjects who receive the Tritanium® Acetabular Shell. This does not include cases censored from analysis or cases that are unavailable for evaluation at the 5-year primary endpoint.

The primary and secondary efficacy analyses will be based on the per protocol population.

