### 12.4 Protection Against Risks

Subjects will be treated in the best medical judgment of the investigator, regardless of the study protocol. If an investigator must deviate from the written protocol to protect the health or wellbeing of the subject, this deviation will be promptly reported to both the EC/IRB and Stryker.

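### The deviation rule in Section 9.4.4.4 can remove revised hips from the 94% test, with no qualifying list, adjudicator, cut-off or blinding to revision status

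*Combined protocol and SAP*

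**What the plan says.** Three sections of the protocol work together.

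- **Section 9.4.4.4 (Censored Cases):** where "a protocol deviation occurs which could affect patient outcome, the data for the affected patient will be censored from the Efficacy and Safety Patient Populations". The next sentence adds: "All cases that fall into this category will be reported separately". Here censoring means removal from the analysis set, not censoring in the time-to-event sense.
- **Section 9.4.4.1 (per protocol population):** the set starts from everyone who received the shell, then "This does not include cases censored from analysis". It also says: "The primary and secondary efficacy analyses will be based on the per protocol population".
- **Section 9.1.4 (Primary Efficacy Analysis):** "If the lower bound of this confidence interval is greater than 94%, the non-inferiority hypothesis will be supported". The limit is that of a 90% interval for the 5-year success rate. The interval method is not named.

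Section 9.4.4.3 defines a modified intent-to-treat population. Enrolled subjects who received the shell "will be included in the survival analysis", and the deviation rule does not name this population. Section 9.1.4 says that the Kaplan-Meier curve will be displayed in addition, without tying a decision to it.

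Section 11.6 lists types of deviation, states that the list is not exhaustive, and does not grade them by likely effect on outcome.

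**The concern.** The exclusion depends on whether a deviation might have affected the outcome, and the outcome is revision. Nothing fixes which deviations qualify, who decides, by when, or whether that person knows the hip's status.

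The sponsor will generally know the status. Section 8.3 requires notification within 24 hours for a reportable event when "The AE required a reoperation of the study hip or a revision of any study hip components". Every case receives the same shell, so there is no treatment blinding that would mask the judgement. Section 12.4 foresees departures "If an investigator must deviate from the written protocol to protect the health or wellbeing of the subject", and these plausibly cluster in complicated cases. A deviation in a revised hip is therefore easier to see as relevant to outcome than the same deviation in a hip that is doing well.

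In a two-arm non-inferiority trial, a per protocol analysis is often kept because it can be the more conservative one. That argument does not carry over to a single group compared with a fixed 94%. Here, losing failures faster than successes pushes the estimate up and makes a false non-inferiority claim more likely.

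**Working it through.** **Inputs.** From Section 9.4.2: assumed success 99%, delta 5 points, power 95%, minimum 142 analysed, 20% loss over 5 years, 177 after loss, 240 implanted. From Section 9.1.4: lower limit of a 90% interval (5% in the lower tail) against 94%. Derived, not stated in the plan: 240 × 0.8 = 192 analysed.

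**1. The plan's own figure.** One-sample normal approximation:

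n0 = [(1.645·√(0.94·0.06) + 1.645·√(0.99·0.01)) / 0.05]² = 122.9.

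With continuity correction: (n0/4)·[1 + √(1 + 2/(n0·0.05))]² = 142.2. This matches the stated 142. The exact power at 142 is 94.5%, with up to 3 revisions allowed.

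**2. One revised hip removed.** The Clopper-Pearson lower limit is the 5% quantile of Beta(x, n − x + 1), with x unrevised hips out of n.

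| Analysed | Revisions | Lower limit | After dropping one revised hip | Lower limit |
|---|---|---|---|---|
| 142 | 4 | 93.67% fail | 3/141 | 94.59% pass |
| 177 | 6 | 93.42% fail | 5/176 | 94.12% pass |
| 192 | 6 | 93.93% fail | 5/191 | 94.57% pass |
| 240 | 9 | 93.55% fail | 8/239 | 94.04% pass |

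The allowed count depends on the interval method. At 192 it is 5 for Clopper-Pearson, 6 for Wilson (94.07%) and 7 for Wald (94.13%). A flip still exists under each: Wilson goes from 93.41% (7/192) to 94.04% (6/191), and Wald from 93.46% (8/192) to 94.10% (7/191). For each of the three methods, one dropped failure flips the result at 94 of the 99 sample sizes from 142 to 240.

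**3. False-pass rate at a true 94%, n = 192.** Revisions F follow Bin(192, 0.06). Each revised hip is kept with probability 1 − r and each unrevised hip with probability 1 − u. The test passes if the kept revisions do not exceed the Clopper-Pearson limit for the resulting n. The fractions u and r are assumptions; the documents give none.

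| u (unrevised excluded) | r (revised excluded) | False-pass rate |
|---|---|---|
| 0 | 0 | 2.4% |
| 5% | 5% | 3.5% |
| 5% | 10% | 5.0% |
| 5% | 20% | 9.7% |
| 5% | 30% | 17.7% (17.6% to 17.7% by simulation) |

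The comparator for outcome-dependent removal is 3.5%, not 2.4%. Excluding 5% regardless of outcome already raises the rate, because both the revision count and n shrink while the allowed count usually stays at 5.

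The direction can be checked by hand. With u = 5% and r = 20%, expected kept revisions are 192 × 0.06 × 0.8 = 9.216 and expected kept unrevised hips are 192 × 0.94 × 0.95 = 171.456. The apparent failure rate is 9.216/180.672 = 5.1% instead of 6%.

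**4. Worst case for a single hip.** If one revised hip is dropped whenever that helps, the error is the probability of at most one revision above the limit. This is 6.8% at 142, 5.4% at 192 and 8.5% at 240, against a nominal 5%.

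**5. How often one hip decides.** At 192 with the exact interval, the chance of exactly 6 revisions is 1.0% if true success is 99%. It is 10.6% at 97.9%, the low end of the literature range in Section 9.4.2, and 16.2% at 97%.

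**The case against.** A reader might infer that the exclusion is decided once revision is known, or that the plan intends failures to be dropped. The documents do not say so. Section 9.4.4.4 sets no time for the decision, and some deviations, such as an eligibility breach or a non-protocol component, are known at or near surgery and could be judged then. The text supports only that a later, unblinded judgement is possible because nothing rules it out.

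There are real safeguards. Removed cases must be reported separately, so a dropped revision would be visible. Deviations go to the sponsor and the ethics board, on a form that records date, type and reason. That fixes when a deviation arose, though not when it was judged relevant to outcome. Many of the listed deviations concern consent or visits and could hardly cause a revision, but the list is open-ended. The survival analysis keeps the removed cases, and Section 7.4 even links the Kaplan-Meier curve to the primary endpoint. Still, no section applies the 94% rule to that curve.

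The size is also conditional. At the planned 99%, about 192 × 0.01 = 2 revisions are expected and a one-hip flip is rare. Excluding 10% of revised hips, twice the unrevised rate, only brings the error to 5.0%, the nominal level. Clear inflation needs 20% to 30%, which no figure in the documents supports. Six revisions in 192 would pass under Wilson or Wald, so a limit of 5 should not be read as the plan's own.

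These objections limit how large and how likely the effect is. They do not remove the route by which a revised hip can leave the confirmatory test.

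**Conclusion.** The point holds as a design weakness, not as evidence of biased conduct. A stated rule with an undefined, outcome-related criterion feeds the only test that carries the 94% decision, and the separate reporting and survival analysis do not govern that decision.

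One removed revision can turn a fail into a pass at nearly every plausible sample size and under each of the three interval methods tried. With 192 hips and an exact interval, the false-pass rate goes from 3.5% under outcome-neutral exclusion to between 5.0% and 17.7% under the assumed differential fractions. These figures rest on 192 analysed hips, a true rate exactly at the 94% bar, the exact interval, and exclusion fractions that are illustrations. The practical risk is small if true success is 99% and material if it is nearer 97% to 98%.

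**What to change.** In Sections 9.4.4.4 and 9.4.4.1, state that no implanted hip is removed from the primary 5-year success analysis because of a protocol deviation.

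Then name the estimate to which the 94% rule applies. The Section 9.4.4.3 population includes hips without known 5-year status, and Section 9.3 allows no imputation, so a simple proportion over all implanted hips cannot be computed. Either of these would do:

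- the 5-year Kaplan-Meier estimate with its 90% interval in the Section 9.4.4.3 population, which handles hips without known status without imputation, on the usual assumption that loss is unrelated to revision risk; or
- the proportion among all implanted hips with known 5-year status plus every hip revised earlier. The last clause should be explicit, because Section 10.3 ends participation at shell revision.

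Name the interval method as well, since the allowed number of revisions depends on it.

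Keep the deviation-excluded set as a sensitivity analysis. Limit it to a prespecified list of deviations fixed at or before surgery, classified blind to revision status before database lock.

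The cost is revised wording and one extra analysis, with no new data collection. The downside is that a few deviating cases stay in the primary rate, which may be slightly less favourable.

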# 10 Study Procedures

### 10.1 Subject Recruitment and Screening

Patients will be recruited at the study centers during preoperative visits through normal referral patterns. All patients recruited for this study will have the capacity to give informed consent. Advertising for the study at each center will be at the discretion of the investigator. See Appendix C for samples of study advertisements. All handouts, brochures, advertisements, etc. must be approved by the IRB prior to the dissemination of any recruitment materials to potential subjects.

#### 10.2 Patient Informed Consent and Guidelines

All patients for this study will be provided a consent form describing this study and providing sufficient information for them to make an informed decision about their participation. The informed consent must contain all elements required by the FDA under 21 CFR Part 50, in addition to any other elements required by state, local and institutional policies. See Appendix D for a copy of the Model Informed Patient Consent. This consent form will be submitted with the protocol for review and approval by the IRB for the study. All patients must provide written consent after having had adequate time to consider their participation in the study. The formal consent of a

patient, using the IRB approved consent form, must be obtained before that patient is submitted to any protocol related procedures that are not part of normal care. Written documentation of consent must be provided on the consent's signature page in addition to a note in the patient medical records indicating the date that consent was obtained. The investigator-designated research professional obtaining the consent must also sign this consent form. The patient or their legal representative should receive a signed copy of the consent according to GCP guidelines.

The procedure for obtaining informed consent is outlined below:

- Use a current IRB approved copy of the consent form.
- Review the consent thoroughly with the patient before having them sign.
- After the patient has consented to the procedures, ensure he/she signs and dates the consent form.
- The person obtaining consent also signs and dates the signature page.
- Provide a copy of the consent to the patient.
- If required, provide the hospital with a copy of the signed consent.
- Maintain the signed original in the patient's study chart.

